## **11.0 Safety Analysis**

### **11.1 General Considerations**

Safety data will be summarized using the safety population.

### **11.2 Analysis of Adverse Events**

Adverse events (AEs) will be coded using the Medical Dictionary for Regulatory Activities (MedDRA). The actual version of the MedDRA coding dictionary will be noted in the clinical study report.

#### **11.2.1 Treatment-Emergent Adverse Events**

Treatment-emergent AEs are defined as any AE with an onset date that is after the first dose of study drug and no more than 30 days after the last dose of study drug. Events where the onset date is the same as the study drug start date are assumed to be treatment-emergent. If an incomplete onset date was collected for an AE, the event will be assumed to be treatment-emergent, unless there is other evidence that confirms that the event was not treatment-emergent (e.g., the event end date was prior to the study drug start date).

#### **11.2.2 Tabulations of Treatment-Emergent Adverse Events**

The number and percentage of subjects with treatment-emergent AEs will be tabulated by primary MedDRA System Organ Class (SOC) and preferred term (PT). The SOCs will be presented in alphabetical order, and the PTs will be presented in alphabetical order within each SOC.

#### **Adverse Event Overview**

An overview of AEs will be presented consisting of the number and percentage of subjects experiencing at least one event for each of the following AE categories:

- Any treatment-emergent AE;

- Treatment-emergent AEs with a "reasonable possibility" of being related to DAAs (GLE/PIB);
- Treatment-emergent AEs of grade 3 or higher;
- Serious treatment-emergent AEs;
- Serious treatment-emergent AEs with a "reasonable possibility" of being related to DAAs (GLE/PIB);
- Treatment-emergent AEs leading to discontinuation of study drug;
- DAA-related treatment-emergent AEs leading to discontinuation of study drug;
- Treatment-emergent AEs of Grade 3 or higher with a "reasonable possibility" of being related to DAAs (GLE/PIB);
- Serious treatment-emergent AEs leading to discontinuation of study drug;
- Treatment-emergent AEs leading to interruption of study drug;
- Treatment-emergent AEs leading to death;
- Deaths.

### **Adverse Event by SOC and PT**

Subjects reporting more than one AE for a given preferred term will be counted only once for that term (most severe/highest grade incident for the severity tables and most related incident for the relationship tables). Subjects reporting more than one AE within an SOC will be counted only once for that SOC. Subjects reporting more than one AE will be counted only once in the overall total.

The following summaries of AEs by SOC and PT will be generated:

- Treatment-emergent AEs;
- Treatment-emergent AEs with a "reasonable possibility" of being related to DAAs (GLE/PIB);
- Serious treatment-emergent AEs;
- Serious treatment-emergent AEs with a "reasonable possibility" of being related to DAAs (GLE/PIB);

- Grade 3 or higher treatment-emergent AEs;
- Treatment-emergent AEs leading to discontinuation of study drug;
- DAA-related treatment-emergent AEs leading to discontinuation of study drug;
- Treatment-emergent AEs of Grade 3 or higher with a "reasonable possibility" of being related to DAAs (GLE/PIB);
- Serious treatment-emergent AEs leading to discontinuation of study drug;
- Treatment-emergent AEs leading to interruption of study drug;
- Treatment-emergent AEs leading to death.

A listing of treatment-emergent adverse events grouped by body system and preferred term with subject numbers will be created.

#### **Adverse Event by PT**

The number and percentage of subjects experiencing treatment-emergent AEs will be tabulated according to PT and sorted by overall frequency. Similar summaries will be provided for Grade 3 or higher treatment-emergent AEs, DAA-related treatment-emergent AEs, DAA-related Grade 3 or higher treatment-emergent AEs, and DAA-related treatment-emergent serious AEs.

#### **Adverse Events by Maximum Severity Grade Level**

Treatment-emergent AEs and DAA-related treatment emergent AEs will be summarized by maximum severity grade level of each PT. Each AE will be assigned a grade level (Grade 1, 2, 3, 4, or 5) by the investigator. If a subject has an AE with unknown severity, then the subject will be counted in the severity grade level category of "unknown," even if the subject has another occurrence of the same event with a severity present. The only exception is if the subject has another occurrence of the same AE with the highest grade level (Grade 5). In this case, the subject will be counted under the "Grade 5" category.

### **Adverse Event by Maximum Relationship**

Treatment-emergent AEs also will be summarized by maximum relationship of each PT to study drug (DAAs), as assessed by the investigator. If a subject has an AE with unknown relationship, then the subject will be counted in the relationship category of "unknown," even if the subject has another occurrence of the same event with a relationship present. The only exception is if the subject has another occurrence of the same AE with a relationship assessment of "Reasonable Possibility." In this case, the subject will be counted under the "Reasonable Possibility" category.

### **Adverse Events of Special Interest**

For the hepatic decompensation/hepatic failure AE of special interest defined below, the number and percentage of subjects experiencing at least one treatment-emergent AE in the search will be presented overall and by SOC and PT. In addition, a listing of treatment-emergent AEs for subjects meeting the search criterion will be provided. For the hepatocellular carcinoma AE of special interest, a listing of all AEs meeting the search criterion will be provided.

- Hepatic decompensation and hepatic failure
  - Treatment-emergent events only
  - Product MedDRA Query (PMQ) of "Hepatic decompensation and hepatic failure"
- Hepatocellular carcinoma
  - All post-baseline cases, treatment-emergent and non-treatment emergent
  - Search based on specific MedDRA preferred terms of hepatocellular carcinoma, hepatic neoplasm, hepatic cancer, hepatic cancer metastatic, and hepatic cancer recurrent.

### **11.2.3 Listing of Adverse Event**

The following listings of AEs will be prepared:

- All serious AEs (from the time the subject signed the study-specific informed consent through the end of the study),
- Treatment-emergent serious AEs,
- Treatment-emergent AEs leading to death,
- Treatment-emergent AEs leading to discontinuation of study drug,
- Treatment-emergent AEs leading to study drug interruption.

### 11.3 Analysis of Laboratory Data

Data collected from central and local laboratories, including additional lab testing due to an SAE, will be used in all analyses. The protocol-defined hematology and clinical chemistry laboratory tests will be summarized.

Some of the laboratory variables are calculated by the laboratory vendor including indirect bilirubin, creatinine clearance, and eGFR by MDRD. The central lab calculates eGFR by MDRD using the following equation, where serum creatinine is measured in mg/dL and age is measured in years:

$$\text{GFR (mL/min/1.73 m}^2\text{)} = 175 \times (\text{Serum Creatinine})^{-1.154} \times (\text{Age})^{-0.203} \times 1.212 \text{ (if Black)} \times 0.742 \text{ (if Female)}.$$

The central lab calculates the estimated creatinine clearance (CrCl) based on the following Cockcroft-Gault formula:

$$\text{CrCl (mL/min)} = [ (140 - \text{age}) \times (\text{weight in kg}) \times (0.85 \text{ if female}) ] / [ \text{serum creatinine (mg/dL)} \times 72 ].$$

#### 11.3.1 Statistical Methods

The baseline value for clinical laboratory tests will be the last non-missing measurement on or before the day of the first dose of study drug. Values on Day 1 must also be before

the time of first dose if time is available. The same baseline value will be used for change to Treatment Period visits and change to PT Period visits.

Mean changes from baseline to each post-baseline visit, including applicable post treatment visits, will be summarized for the overall safety population. Each protocol-specified laboratory parameter will be summarized with the sample size, baseline mean, visit mean, change from baseline mean, standard deviation, minimum, median, and maximum.

Changes in the laboratory parameters listed in Section 11.3.1 will be tabulated using shift tables. Laboratory data values will be categorized as low, normal, or high based on the normal ranges of the laboratory used for each sample. A shift table from baseline to minimum value and maximum value during the Treatment Period will be created. In this shift table, the number and percentage of subjects with baseline values within or above the normal range (baseline high or normal) and a minimum value below the normal range (post-baseline low) and the number and percentage of subjects with baseline values within or below the normal range (baseline low or normal) and a maximum value above the normal range (post-baseline high) will be summarized.

Child-Pugh scores will be categorized as 5, 6, > 6, or missing at baseline and each protocol-specified post-baseline visit, including applicable post-treatment visits. Shift tables from baseline to each post-baseline visit will be created. The shift tables will cross-tabulate the frequency of subjects with baseline values in each category versus the post-baseline categories. For each baseline category and across the baseline categories, the percentage of subjects in each post-baseline category (excluding the post-baseline category of missing) will be calculated.

The laboratory parameters defined in Table 7 will be assigned a toxicity grade of 1, 2, 3, or 4. The number and percentage of subjects with a maximum toxicity grade of 1, 2, 3 or 4 will be summarized. The post-baseline value must be in a toxicity grade that is more extreme than the toxicity grade corresponding to the baseline value in order to be counted. The summary will also include the number and percentage of subjects with a maximum of

at least Grade 3 for all laboratory parameters in Table 7. A listing of all relevant laboratory parameters will be provided for each subject who had an increase to Grade 2 or higher for all laboratory variables in Table 7.

**Table 7. Definitions of Toxicity Grades 1, 2, 3, and 4 for Laboratory Values**

Test	Grade 1	Grade 2	Grade 3	Grade 4
ALT/SGPT	> ULN – 3 × ULN	> 3 – 5 × ULN	> 5 – 20 × ULN	> 20 × ULN
AST/SGOT	> ULN – 3 × ULN	> 3 – 5 × ULN	> 5 – 20 × ULN	> 20 × ULN
Alkaline Phosphatase	> ULN – 2.5 × ULN	> 2.5 – 5 × ULN	> 5 – 20 × ULN	> 20 × ULN
Total Bilirubin	> ULN – 1.5 × ULN	> 1.5 – 3 × ULN	> 3 – 10 × ULN	> 10 × ULN
Hemoglobin	< LLN – 100 g/L	< 100 – 80 g/L	< 80 g/L	--
Absolute Neutrophil Count	< LLN – 1.5 × 10  /L	< 1.5 – 1.0 × 10  /L	< 1.0 – 0.5 × 10  /L	< 0.5 × 10  /L
Platelet count	< LLN – 75.0 × 10  /L	< 75.0 – 50.0 × 10  /L	< 50.0 – 25.0 × 10  /L	< 25.0 × 10  /L
INR	> 1 – 1.5 × ULN	> 1.5 – 2.5 × ULN	> 2.5 × ULN	--
Creatinine clearance	< LLN – 60 mL/min	< 60 – 30 mL/min	< 30 – 15 mL/min	< 15 mL/min
Albumin	< LLN – 30 g/L	< 30 – 20 g/L	< 20 g/L	--

### **Assessment of Hepatic Laboratory Values**

The number and percentage of subjects with laboratory values meeting the following criteria during treatment will be summarized:

- Post-nadir (preceding value is lower than the subsequent value) ALT > 5 × ULN (regardless of grade change);
- Total bilirubin ≥ 2 × ULN and > baseline (i.e., a post-baseline value must be more extreme than the baseline value to be considered);
- Post-nadir ALT > 3 × ULN and total bilirubin > 2 × ULN;
- Post-nadir ALT > 3 × ULN and total bilirubin ≤ 2 × ULN.

Four listings (one for each bullet above) of all liver function tests including ALT, AST, total, indirect and direct bilirubin, ratio of direct to total bilirubin, and alkaline phosphatase values will be provided for each subject who met the criterion defined above.

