AEs and AEs leading to premature study drug discontinuation were rare. Adverse events that are known, and those that may potentially occur with GLE/PIB are described in the informed consent form for this study. In addition, subjects may experience inconvenience or discomfort related to the study visits or study procedures. Additional safety data for each DAA alone and the combination of GLE/PIB are detailed in Section 3.0 and in the Investigator's Brochure.¹²

No significant trends in liver chemistry abnormalities have been observed in Phase 2 and 3 studies, including patients with compensated cirrhosis.

The overall rates of virologic failure for the GLE/PIB regimen in Phase 2 and 3 studies were low. With the shortened duration of treatment in this study, higher rates of virologic failure may be observed. In patients who experience virologic failure, amino acid substitution(s) in NS3 and/or NS5A conferring resistance to GLE and/or PIB, respectively, may emerge. NS3 substitutions tend to revert back to wild type, while NS5A substitutions have been reported to persist for years. Retreatment of subjects who experience virologic failure with the GLE/PIB regimen for 8 weeks will be offered in the AbbVie Study M15-942.

An assessment of the post-treatment relapse rate occurring in this study in the non-GT3 and in the GT3 population will be performed on a periodic basis in order to minimize exposure to a potentially suboptimal duration (see Section 5.4.1.2).

Based on results of Phase 1 pharmacokinetic studies clinically significant DDI's with GLE/PIB have been identified. Monitoring of subjects, with dose adjustment of concomitant medications, as well as exclusion of subjects requiring the use of prohibited medications is expected to mitigate this risk. Hepatitis B virus reactivation has been reported as a pharmacological class risk for DAAs. This risk will be mitigated by proper screening and surveillance for HBV as described in the protocol.

Risks associated with GLE/PIB including the risks of toxicity, virologic failure, and development of resistant mutations substitutions (Section 5.6.4.3) appear to be limited and manageable based upon the available data.

Overall, given the potential for achieving SVR₁₂ with 8 weeks of treatment in this population of HCV GT 1 - 6 infected subjects with compensated cirrhosis, the risk-benefit assessment is considered favorable.

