5.2.2 Exclusion Criteria

A subject will not be eligible for study participation if he/she meets any of the following criteria:

1. Female subject who is pregnant, breastfeeding or is considering becoming pregnant during the study or for approximately 30 days after the last dose of study drug.
2. HCV genotype performed by the central laboratory during screening indicating co-infection with more than one HCV genotype.
3. Current HBV or HIV infection on screening tests, defined as:
 - A positive HBsAg, or;
 - HBV DNA > LLOQ in subjects with isolated positive anti-HBc (i.e., negative HBsAg and Anti HBs), or;
 - A positive anti human immunodeficiency virus antibody (HIV Ab).
4. Requirement for and inability to safely discontinue the medications or supplements listed in Table 4 at least 14 days or 10 half-lives (whichever is longer) prior to the first dose of any study drug.
5. Clinically significant abnormalities or co-morbidities, or recent (within 1 year prior to study drug administration) alcohol or drug abuse that make the subject an unsuitable candidate for this study in the opinion of the investigator.
6. Any current or historical clinical evidence of decompensated cirrhosis, including any current or past evidence of Child-Pugh B or C classification, hepatic encephalopathy or variceal bleeding, radiographic evidence of small ascites, or empiric use of lactulose/rifaximin for neurologic indications. The use of beta blockers is not exclusionary.
7. Screening laboratory analyses showing any of the following abnormal laboratory results:
 - Alanine aminotransferase (ALT) > 10 × ULN
 - Aspartate aminotransferase (AST) > 10 × ULN
 - Total Bilirubin > 3.0 mg/dL
 - Calculated creatinine clearance (CrCl, Cockcroft-Gault method) < 50 mL/min
 - Albumin < 2.8 mg/dL
 - Hemoglobin < 10 g/dL

- Platelets < 50,000 cells/mm³
- 8. Receipt of any investigational or commercially available anti-HCV agents, including direct acting antivirals (e.g., interferon, ribavirin, sofosbuvir, telaprevir, boceprevir, simeprevir, paritaprevir, grazoprevir, voxilaprevir daclatasvir, ledipasvir, ombitasvir, elbasvir, velpatasvir, or dasabuvir).
- 9. History of severe, life-threatening or other significant sensitivity to any excipients of the study drug.
- 10. Subject who cannot participate in the study per local law.

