| Lymphocytes | Alanine aminotransferase (ALT) ^b | Anti-HAV IgM ^f |
| Monocytes | Aspartate aminotransferase (AST) | Anti_HAV Total ^f |
| Basophils | Alkaline phosphatase | Anti-HEV IgG ^f |
| Eosinophils | Sodium | Anti-HEV IgM ^f |
| Platelet count (estimate not acceptable) | Potassium | HEV RNA ^f |
| Reticulocyte count | Calcium | Anti-HBc IgM ^f |
| Prothrombin Time/INR ^a | Inorganic phosphorus | HBV DNA ^g |
| Activated partial thromboplastin time (aPTT) | Cholesterol | IL28B ^h |
| Urine Drug/Alcohol Screen^c | | HCV genotype and subtype ^c |
| Opiums | Total protein | Pharmacogenetic sample (optional) |
| Barbiturates | Glucose | Alpha2-macroglobulin ^b |
| Amphetamines | Triglycerides | Haptoglobin ^b |
| Cocaine | Albumin ^a | Apolipoprotein A1 ^b |
| Benzodiazepines | Chloride | |
| Phencyclidine | Bicarbonate | |
| Propoxyphene | Magnesium | |
| Alcohol | Gamma-glutamyl transferase (GGT) ^b | |

- a. Also a component of Child-Pugh Assessment.
- b. Also a component of FibroTest.
- c. Performed only at Screening.
- d. Required only for females of childbearing potential.
- e. Performed at Screening for all subjects and also performed for management of transaminase elevation (Section 6.1.7.1).
- f. Performed for management of transaminase elevation (Section 6.1.7.1).
- g. Performed at Screening for subjects who have occult HBV infection (positive Anti-HBcAg with negative HBsAg and Anti-HBs) and also performed for management of transaminase elevation (Section 6.1.7.1).
- h. Performed only at Baseline.

For any laboratory test value outside the reference range that the investigator considers to be clinically significant:

- The investigator will repeat the test to verify the out-of-range value.
- The investigator will follow the out-of-range value to a satisfactory clinical resolution.
- A laboratory test value that requires a subject to be discontinued from the study or study drug or requires a subject to receive treatment will be recorded as an adverse event.

The management of laboratory abnormalities that may occur during the study is described in Section [6.1.7](#).

Pregnancy Testing

- WOCBP must have a negative serum pregnancy test result at Screening, and a negative urine pregnancy test at Study Day 1.
- If urine pregnancy test is positive at any time, a serum pregnancy test should be performed.

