Appendix D. Study Activities – Post-Treatment Period

| Activity | PT Wk 4 | PT Wk 12 | PT Wk 24 or PT D/C ^a |
|---|---------|----------------|---------------------------------|
| Vital Signs and Weight | X | X | X |
| Hematology/Chemistry/Coagulation Panel | X | X ^b | X ^b |
| Pregnancy Test (urine [u]) ^c | X (u) | | X (u) ^a |
| Concomitant Medication Assessment ^d | X | X ^d | X ^d |
| Adverse Event Assessment ^e | X | X ^e | X ^e |
| HCV RNA Samples | X | X | X |
| HCV Resistance Sample | X | X | X |
| Pharmacogenetic DNA and RNA Sample (optional) | | X | |
| Archive Plasma and Serum Sample | X | X | X |
| FibroTest and APRI | | X | X |
| Child-Pugh Score | | X | X |
| Physical Exam ^h | | X | X |
| HCC Screening Liver Ultrasound | | | X ⁱ |
| Patient Reported Outcomes Instruments (PROs) ^{f,g} | | X | X |

Wk = Week; PT D/C = Post-Treatment Discontinuation

- Subjects who prematurely discontinue from the Post-Treatment Period should return to the site to complete the PT D/C Visit procedures. Hematology/Chemistry/Coagulation Panel and Pregnancy Test are not required at PT Wk 24 but at PT D/C only if subject discontinues prior to PT Wk 4.
- Hematology/Chemistry/Coagulation Panel drawn at PT Wk 12 and PT Wk 24 are only conducted to support Child-Pugh assessment and/or FibroTest and APRI determination. No other analytes will be resulted as part of the labs drawn at these timepoints.
- Pregnancy testing is not required in the PT period for women that are not of childbearing potential.
- Only medications taken for SAEs and for treatment of HCV will be collected after 30 days post-dosing.

- e. Nonserious AEs and all SAEs will be collected until 30 days post dosing. All spontaneously reported SAEs will be collected thereafter; nonserious AEs will not be collected (see Section [6.1.4](#)).
- f. PROs should be administered before any study procedures and in the order listed in Section [5.3.1.1](#).
- g. TSQM should not be collected in the post-treatment period.
- h. An abbreviated Physical Exam should be conducted to assess Ascites, and potential hepatic encephalopathy required for the Child Pugh assessment score.
- i. Please refer to Section [5.3.1.1](#) item "Hepatocellular Carcinoma Screening Liver Ultrasound" for details on this study procedure.

Note: Day 1 of the Post-Treatment Period will be defined as the day after the last dose of study drug.

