### **Hepatic Laboratory Abnormalities of Interest**

Among the events assessed under "Assessment of Hepatic Laboratory Values," the following criteria are of interest:

- Confirmed post-nadir ALT > 5 × ULN;
- Post nadir ALT > 3 × ULN and a concurrent total bilirubin > 2 × ULN with a direct bilirubin:total bilirubin ratio > 0.4.

To support the assessment of hepatic laboratory abnormalities of interest, the following potential events will be summarized:

- Confirmed post-nadir ALT > 5 × ULN;
- Post-nadir ALT > 3 × ULN and total bilirubin > 2 × ULN and direct/total bilirubin ratio > 0.4.

Two listings (one for each bullet) of all liver function tests including ALT, AST, total, indirect and direct bilirubin, ratio of direct to total bilirubin, and alkaline phosphatase values will be provided for each subject who met the criterion defined above.

For the assessments of hepatic laboratory values and hepatic laboratory abnormalities of potential interest, the maximum ratio relative to the ULN will be used to determine if subjects meet any of the criteria listed above. The ALT and total bilirubin values do not need to be concurrent in order to meet the defined criteria in statistical summaries. For ALT, the post-baseline value must represent an increase from the first nadir (including baseline) to be counted. First nadir is defined as the last value prior to the first increase. For total bilirubin, a subject will be counted if the post-baseline laboratory value meets the above criteria regardless of the baseline laboratory value (i.e., the post-baseline laboratory value does not need to be worse than the baseline laboratory value), except where noted

above. A confirmed post-nadir increase in ALT is defined as two consecutive values of ALT > 5 × ULN after nadir, either both during treatment or at the final treatment measurement and the next consecutive post-treatment measurement. A single post-nadir ALT value of greater than 5 × ULN followed by lost to follow-up (no additional ALT values) also will be considered as confirmed (i.e., will not require confirmation). The ratio of direct to total bilirubin will be calculated using the same date/time sample corresponding to the total bilirubin elevation.

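### The SAP reports no HBV serology or post-baseline HBV results, and its hepatic ALT/bilirubin criteria count only rises that begin on treatment

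*SAP*

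**What the plan says.** Protocol 3.2 states: "Hepatitis B virus reactivation has been reported as a pharmacological class risk for DAAs". It continues: "This risk will be mitigated by proper screening and surveillance for HBV as described in the protocol".

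Protocol 5.2.2 excludes HBsAg-positive subjects and "HBV DNA > LLOQ in subjects with isolated positive anti-HBc". Other anti-HBc-positive subjects are not excluded on that ground. Under Protocol Table 5 (footnote g), HBV DNA is screened only in subjects with isolated anti-HBc.

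After Screening, HBV testing is tied to ALT. Footnote e of Table 5 describes the hepatitis B panel as "Performed at Screening for all subjects and also performed for management of transaminase elevation". The work-up in Protocol 6.1.7.1, which includes HBsAg and HBV DNA, follows any confirmed post-baseline ALT above 5 × ULN that is also above twice baseline. It is not limited to the treatment period.

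SAP 11.3.1, Assessment of Hepatic Laboratory Values, says: "The number and percentage of subjects with laboratory values meeting the following criteria during treatment will be summarized". Under Hepatic Laboratory Abnormalities of Interest, a confirmed rise needs two consecutive ALT values above 5 × ULN, "either both during treatment or at the final treatment measurement and the next consecutive post-treatment measurement".

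Protocol Appendix D schedules a chemistry panel at PT Week 4, and FibroTest with APRI at PT Weeks 12 and 24. The panels at those two later visits "are only conducted to support Child-Pugh assessment and/or FibroTest and APRI determination".

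**The concern.** The protocol names a specific harm, relies on surveillance to contain it, and collects the results that would reveal it. The SAP has no place for those results. HBV appears neither among the baseline characteristics (SAP 7.1) nor among the subgroups (SAP 10.6). The only events of special interest are hepatic decompensation/failure and hepatocellular carcinoma (SAP 11.2.2). SAP 11.3 summarises hematology and clinical chemistry tests, whereas Protocol Table 5 puts the hepatitis B panel and HBV DNA under other tests.

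The criteria best suited to finding a flare, those based on post-nadir ALT, stop at the end of treatment, although follow-up runs 24 weeks further. Safety is one of the two primary objectives (Protocol 4.1), and the reports are meant to support labelling changes (SAP 4.4.2). At stake is whether those reports can describe flares and HBV results that the trial itself measured.

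**Working it through.** The plan gives no figure to reproduce. The check sets measurement against reporting.

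**1. Window arithmetic (8-week completer).** Treatment is 56 days and follow-up 168 days, 224 in all.
- SAP Table 1 closes treatment windows at Study Drug End Day 2: (56 + 2)/224 = 58/224 = 26%. This leaves 166 of the 168 post-treatment days outside.
- Treatment-emergent AEs run to 30 days after the last dose: (56 + 30)/224 = 86/224 = 38%. In the remaining 168 − 30 = 138 days only spontaneously reported SAEs are collected (Protocol 6.1.4).
- Scheduled post-baseline ALT: Weeks 1, 2, 4 and 8, then PT Weeks 4, 12 and 24, so 3 of 7 are off treatment. ALT at PT Weeks 12 and 24 is inferred from Table 5, which marks ALT and total bilirubin as FibroTest components. Direct bilirubin is not so marked.

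These are shares of calendar time and of draws, not probabilities of missing an event.

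**2. Where a post-treatment flare would appear.**

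| Output | Post-treatment flare shown? |
|---|---|
| Hepatic criteria and their listings (SAP 11.3.1) | No, unless ALT was already high at the final treatment measurement |
| Low/normal/high shift tables (SAP 11.3.1) | No; limited to the Treatment Period |
| Table 7 grades and Grade 2+ listing (SAP 11.3.1) | SAP sets no treatment limit; Protocol 8.1.5.2 can be read as setting one. Counts only a grade worse than baseline |
| Change from baseline by visit (SAP 11.3.1) | A maximum is reported at post-treatment visits, without subject identity |
| Treatment-emergent AE tables and listing (SAP 11.2) | Yes, if recorded as an AE by day 30 |
| SAE listing (SAP 11.2.3) | Yes, if reported as serious, to end of study |
| HBsAg and HBV DNA results | No table or listing |

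**3. A worked subject.** Protocol 5.2.2 allows screening ALT up to 10 × ULN. Take baseline ALT 6 × ULN, normal at end of treatment, then a confirmed 15 × ULN at PT Week 12.
- Protocol 6.1.7.1: 15 > 5 and 15 > 2 × 6 = 12, so HBV DNA and HBsAg are obtained.
- Hepatic criteria: the rise did not begin on treatment, so it is not counted.
- Table 7: Grade 3 is above 5 to 20 × ULN, so the change is Grade 3 to Grade 3 and is not counted, even if post-treatment values are admitted.
- AE route: day 84 is past day 30, so a non-serious event is not collected. Medications are by then recorded only for HCV or SAEs (Protocol 5.2.3).

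More generally, for baseline b above 5 and below 10 × ULN, a post-treatment value above 2b and up to 20 × ULN triggers the work-up but adds nothing to Table 7.

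**4. Denominator (illustration only).** The documents give no anti-HBc prevalence. If it were 10% to 40% of 330, that is 33 to 132 subjects. With zero events, the one-sided 95% upper bound 1 − 0.05^(1/n) is 8.7% for n = 33 and 2.2% for n = 132, against 0.9% for n = 330.

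**The case against.** The strongest reply is that other outputs cover much of this ground. SAP 11.3.1 places no treatment limit on the Table 7 grades, although it does on the shift tables in the same section. Its Grade 2+ listing starts at ALT above 3 × ULN, lower than the 5 × ULN criterion. In Protocol 8.1.5.2 the treatment restriction may attach only to the laboratory parameters of interest. The visit-wise change tables include post-treatment visits and report a maximum, so one large rise could show there. PT Week 4 (nominal day 28) lies within the treatment-emergent AE period, and investigators may record a laboratory abnormality as an AE. The hepatic wording was aligned across the Phase 3b programme (SAP 12.1).

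All of this stands. A reader might infer that HBV reactivation could pass wholly unreported, or that every ALT summary stops with treatment. The documents support neither inference. An AE search over all post-baseline time would also add little: beyond day 30 only SAEs are collected, and these are already listed.

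Two limits on any remedy also stand. Retesting follows only an ALT rise, so a rate in anti-HBc-positive subjects describes detected events and not all reactivation. And the direct/total bilirubin ratio cannot be expected at PT Weeks 12 and 24.

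The reply does not supply a place for the HBV results. Nor does it bring the worked subject into the hepatic criteria or Table 7.

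**Conclusion.** The point holds within limits. The SAP reports neither who was at risk of reactivation nor what the HBV tests showed, and its post-nadir ALT and bilirubin criteria drop rises that begin off treatment. The exposed cases are non-serious or unrecognised flares after treatment, chiefly after day 30 (the last 138 of 224 planned days) or in subjects with raised baseline ALT. Such cases can be missing from the hepatic-criteria tables and listings. Whether Table 7 counts them depends on an unsettled window and, for baseline ALT above 5 × ULN, on the grade rule.

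This rests on ALT and total bilirubin being resulted with FibroTest at PT Weeks 12 and 24, and on HBV results reaching the clinical database. The protocol says that HIV results will not be reported there but states no such exception for HBV. The number of subjects affected cannot be estimated from the documents, and the bounds above depend on an assumed prevalence. The change is worth making before the analyses are run. It does not touch the efficacy conclusions.

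**What to change.** 1. In SAP 11.3.1, apply the post-nadir ALT and total bilirubin criteria, including the confirmed rule, separately to the Treatment Period and the Post-Treatment Period (Study Drug End Day > 2). Show relapse and new HCV treatment status beside each post-treatment case. Apply the direct/total bilirubin ratio only where direct bilirubin is resulted.
2. In SAP 7.1, add screening anti-HBc/anti-HBs status. Add a by-subject listing of all post-baseline HBsAg and HBV DNA results with concurrent ALT. Show counts over anti-HBc-positive subjects as well as the safety population, labelled as ALT-triggered detected events.
3. State whether Table 7 and its Grade 2+ listing include post-treatment values, and reconcile SAP 11.3.1 with Protocol 8.1.5.2.

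The cost is SAP wording, some table columns and a listing from data the protocol already collects. No visit, sample or clinical rule changes. The downside is that post-treatment ALT rises unrelated to drug, such as those with relapse, will also appear, which is why relapse status belongs beside them.
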